4.4. Data collection

Infants meeting all of the inclusion criteria will have *de-identified* information collected on selected characteristics of mother, delivery and infant. This information will allow a comparison of randomised and non-randomised infants to determine the impact on generalizability of exclusions, infants where consent was not sought for some reason, and infants where consent was refused. Infants that are randomised will also have their randomisation number recorded on the form, allowing linkage to data collected in the study. Annex A lists the variables on which data will be collected on infants meeting all inclusion criteria.

Infants that are randomised will have additional detailed information collected on the course of treatment, and on all key primary and secondary outcomes. Annex B lists the variables on which data will be collected on randomised infants.

Information from the data collections forms will be entered into a password protected online database operated by the Australian Pediatric Trials Network ('WebSpirit') which will be accessed through the Ramaiah Hospital computer network, accessible to study administrators; the database includes an FDA-compliant audit mechanism which tracks all data queries and modifications after initial entry. The database will not contain any names or addresses, only Study ID numbers and Medical Record Numbers (MRNs). A listing of Study ID numbers will be linked to names, addresses and contact numbers in paper records kept in a locked filing cabinet in the Medical Records Department of Ramaiah Medical College, until results are published.

4.5. Measurement of outcomes

As blinding to exposure is not possible, it is important that steps are taken to prevent differential measurement error. Thus, the following steps will be taken to ensure consistency of measurement in the two treatment arms:

Primary outcome:

FiO₂ is measured on the CPAP machines themselves, which creates a possibility of differential error. The oxygen readings for the study will be algorithmically or arithmetically calibrated prior to analysis, based on measurement of FiO₂ as the gas exits the patient interface, to identify if there are any systematic differences in the reported FiO₂ being provided and the actual FiO₂ delivered to the patient interface; this will be done prior to study commencement and at the end of the first, third, fifth and seventh months after commencement. The AAI model PSR-11-917-MH oxygen analyser will measure the FiO₂ delivered against that reported by each CPAP machine across the full range of FiO₂ (21%, 25%, 30%, 35%, and every 10% from 40%-99%).

Secondary outcomes:

- SpO₂: SpO₂ will be measured using the same stand-alone pulse oximeters in both the intervention and control arms (i.e., ignoring the built-in pulse oximeter on the new CPAP to prevent differential measurement error) – both groups will be monitored using the Mindray multichannel monitor (MEC 3000), placed on the right hand/arm (i.e., pre-ductal) in line with a standardised SpO₂ measurement protocol developed for the study, which will apply to both treatment groups;
- Respiratory rate: A standard measurement protocol will be developed and introduced which requires measurement of respiratory rate over 30 seconds at 0, 6, 24, 48 and 72 hours, doubling this number to achieve a rate per minute. The protocol will outline the conditions under which measurement is to take place, and the extent to which measurement can be deferred if an infant has a temporarily elevated respiratory rate due, for example, to crying;
- Arterial blood gases: A standard measurement protocol will be introduced which governs the process for taking arterial blood samples at 0, 6, 24, 48 and 72 hours. If blood samples

are not required for clinical management, they will be ceased, so not all readings will be performed for all babies.

- Damage to septum: A standard measurement protocol will be introduced which governs the process for diagnosing damaged septum;
- Damage to nares: A standard measurement protocol will be introduced which governs the process for diagnosing damaged nares;
- Pneumothorax: The treating clinician will order and interpret the X-ray for clinical purposes, but the X-rays will be provided to the radiologist for independent verification, blinded to treatment arm;
- IVH/ICH/PVL: The consultant radiologist will undertake the scans for IVH/ICH/PVL, but it is not possible to blind to study allocation.
- $\text{FiO}_2 \geq 60\%$: This is made objective by having the same saturation targeting protocol for both treatment groups (90-95% by SpO_2), and by requiring that the oxygen requirement is maintained for one hour or more;
- Intubation & ventilation: This may be subjective and will therefore be interpreted alongside the objective indicator of a high oxygen requirement ($\geq 60\%$ for ≥ 1 hour);
- Surfactant: This may be subjective and will therefore be interpreted alongside the objective indicator of a high oxygen requirement and chest X-Ray result ($\text{FiO}_2 > 40\%$ to achieve 90-95% SpO_2 , with chest X-Ray suggestive of RDS); and
- Death prior to hospital discharge: This is an objective indicator unless infants are routinely discharged home moribund, which occurs in some low resource settings (to avoid mortuary costs), but which is not practised at Ramaiah Medical College.

4.6. Safety and significant adverse events

A subset of the sentinel events being evaluated as secondary outcomes will also be monitored as adverse events during the course of the study. These, include:

- Damage to the nasal septum;
- Damage to the nares;
- Pneumothorax as diagnosed by X-Ray;
- IVH/ICH/PVL as diagnosed by cranial ultrasound;
- Intubation and mechanical ventilation; and
- Death prior to hospital discharge.

Adverse events will be referred to the Chief Investigator as they occur to allow ongoing monitoring, and corrective action if required. A Data Safety Monitoring Board (DSMB) is not proposed, as the small number of randomised infants in the trial (40 per arm) mean that the anticipated number of adverse events are expected to be too small for meaningful analysis. If an unusual group of events is noted, the Chief Investigator can choose to suspend randomisation and convene a DSMB.

4.7. Trial funding

Funding is being provided through Thrive Networks, which is in receipt of funding from the Wellcome Trust under the R&D for Affordable Healthcare in India scheme. The purpose of this project, entitled “Continuous Positive Airway Pressure (CPAP) machine to promote rational oxygen use for neonates and to reduce the incidence of retinopathy of prematurity (ROP)” is to develop and commercialise a low-cost CPAP machine for the Indian marketplace.

5. Sample size and statistical analysis:

5.1. *Sample size calculation*

Sample size calculations are based on the primary outcomes. All the outcomes are selected to be continuously distributed. A sample size of 40 infants per group has been selected as something that is achievable at the anticipated recruitment rate at Ramaiah Hospital in the time available (10 months, including 8 months for recruitment at 10 randomised infants/month). The trial will cease when 40 infants have been randomised to each arm (i.e., at this point the other arm must have 40 or more randomised infants). With this sample size, a difference of 0.63 standard deviations is detectable, with 80% power ($1-\beta$) and a 5% false-positive rate (α). We lack data, within the study population, on the anticipated outcomes in the primary and secondary endpoints.

Feasibility: An assessment of eligible infants meeting the inclusion criteria (and none of the exclusion criteria) in February and March 2016 (two complete months) identified:

- 24 inborn neonates eligible for randomisation (i.e., 12/month); and
- 11 outborn neonates admitted to Ramaiah <6 hours of age (i.e., 5.5 /month).

This give a total of 17.5 eligible infants per month. Previous experience at Ramaiah is reported to be a 70% recruitment rate which, if maintained in the current study, would yield an average of 12.2 randomised infants/month. This is above the required randomisation rate of 10 infants per month, and suggests that the project would be feasible with a 60% recruitment rate.

5.2. *Statistical analysis*

Primary and selected secondary outcomes - descriptive: The raw values of the primary outcome (FiO_2) and five secondary outcomes (SpO_2 , respiratory rate, pH, PaO_2 , PaCO_2) will be graphed to allow visual comparison of differences at baseline and over time.

Primary outcome: With longitudinal measurement, the interpretation of later results can be impacted by differential losses before 72 hours (death or intubation and ventilation). Analysis will therefore commence with a Kaplan-Meier curve comparing 'loss' (death or intubation and ventilation), and an associated Cox regression model to compare the rate of loss in the two treatment arms. The results of this survival analysis will provide the context within which the longitudinal results will be interpreted. If there are differential losses over time, the least affected time point will be 6 hours after treatment commencement, and this time point will be promoted to being the primary outcome. If losses over time are not differential, the planned analysis is described below.

The preferred omnibus analysis is a longitudinal mixed effects model (using PROC MIXED in SAS 9.4), controlling for baseline through a random 'intercept', in line with international recommendations for controls on baseline.^[30] Individual analyses at each time point (6, 12, 24, 48, and 72 hours) will be by multiple regression, again adjusting for baseline as a covariate.^[30] If multiple regression model requirements for normality and homoscedasticity are not met, analysis will be by t-test which is known to be robust to violations of the normality assumption, and will be based on the change in variable from baseline value, providing some control for different baselines, but without the additional control offered by multivariate analysis.

Where performed, multivariate analysis will control for stratification; if univariate analysis is used, separate stratum-specific sub-analysis will be undertaken, and a stratified t-test will be performed. Additional covariates will be adjusted for in multivariate analysis, if the baseline comparison shows substantial group difference in significant prognostic factors (e.g., onset of labour is associated with the stimulation of surfactant production, so analysis will control for mode of delivery if there is a clinically relevant mal-distribution).

Secondary outcomes: Five of the secondary outcomes (SpO_2 , respiratory rate, pH, PaO_2 , PaCO_2) will be analysed using the same procedures as for the primary outcome. It is anticipated that the three arterial blood gases (pH, PaO_2 , PaCO_2) will not be performed on all infants, particularly infants that recover rapidly; if so, this analysis will be restricted to change from baseline at the 6-hour reading.

Duration of CPAP (hours), for those not failing CPAP treatment, is the only continuous secondary outcome this is expected to be non-normally distributed and will therefore be assessed using Wilcoxon's rank sum test, with stratum-specific contributions aggregated using Elteren's extension to the Wilcoxon test.^[31]

The remaining secondary outcomes are dichotomous and will be tabulated and compared using stratum-specific relative risks (RRs); the homogeneity of stratum-specific RRs will be assessed using Cochran's Q and the I^2 tests^[32].

Software: All analysis will be conducted in SAS/STAT® 9.4, except for the calculation of stratum-specific and pooled relative risks, which will be performed in RevMan 5.3.^[33]

6. **Clinical protocol:**

6.1. **Interventions**

This study compares routine CPAP care on existing machines with CPAP care on a new machine that uses a re-usable humidifier and tube set.

Routine CPAP care will be on a Fisher & Paykel [FP] CPAP machine which includes separate oxygen and medical air intakes, a FP blender, and a disposable FP humidification chamber and tube set including a heater wire (Fisher & Paykel Healthcare Ltd, Auckland, New Zealand; hereafter referred to as FP CPAP). The new machine (hereafter referred to as the 'Dolphin CPAP') includes an oxygen intake, an on-board air compressor, built in Massimo pulse oximeter (not used in this study – see para 4.5 above), and an autoclavable humidifier and tube set.

6.2. **Treatment protocol features that are common to both arms**

The following systems will be common to both groups regardless of treatment allocation:

- Baby interface: An identical FP infant interface will be used for both groups of babies; this may require the creation of a special adaptor to permit use of the FP interface with the Dolphin CPAP tube set if the FP interfaces for non-FP connectors is not identical to the FP interface for FP tube sets;
- Pulse oximetry: The FP CPAP does not include built-in pulse oximetry, while the Dolphin CPAP does. To ensure consistency in measurement of pulse oximetry, Ramaiah Medical College will use a single pulse oximeter (built into the Mindray MEC 3000), for monitoring SpO₂ on all infants regardless of the treatment allocation. This ensures that any measurement error in SpO₂ will be non-differential.

A standard clinical protocol will be prepared for the study, based on existing clinical practice at Ramaiah Medical College, which will apply equally to both treatment groups. The clinical protocol will specify:

1. Standard prong sizes to be used, by infant weight;
2. The SpO₂ range to be targeted;
3. The timing of obligatory outcome measurements (baseline, 6, 12, 24, 48 and 72 hours) and how they should be conducted, and how measurement complications should be managed if they arise (e.g., how long to delay with scheduled measurement of respiratory rate if infant is crying; how to address missed measurement) – this includes:
 - a. FiO₂;
 - b. SpO₂;
 - c. Respiratory rate; and
 - d. Arterial blood gasses, including pH, PaO₂, and PaCO₂.
4. Procedures governing the diagnosis and treatment of all adverse events, specifically:
 - a. Identification and confirmation of damage to the septum and nares;
 - b. Determining the need for screening for pneumothorax, and the process for blinded verification; and
 - c. Determining the need for cranial ultrasound, and the process for (unblended) diagnosis of IVH or ICH or PVL.
5. A clinical algorithm for managing all aspects of CPAP provision, including:
 - a. FiO₂ and PEEP, including starting points and rules governing stepping up and stepping down of these (including order, and size of increment);
 - b. Transfer to intubation and ventilation; and/or
 - c. Weaning from CPAP; and/or
 - d. Rules covering re-commencement of CPAP.

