- a. As with the primary endpoint, change from baseline at the 6-hour reading was adopted as the preferred analysis for SpO₂ (Secondary outcome #2), respiratory rate (Secondary outcome #3), pH, PaO₂, PaCO₂ (all reported as part of Secondary outcome #4) and duration of CPAP (Secondary outcome #8). Due to concerns about non-normality, van Elteren's extension to the Wilcoxon test was used to assess statistical significance, while controlling for stratification by gestational age group. No testing was performed for Secondary outcome #4 (pH, PaO₂, PaCO₂) as there were only five infants who had readings at both baseline and six hours of age.
- b. Dichotomous secondary outcomes were compared using the Cochran-Mantel-Haenszel test, with assessment for homogeneity using the Breslow-Day test. The exceptions to this were:
 - Where there were no events in one stratum (i.e., CPAP failure [Secondary outcome #5], Serious Adverse Event [Secondary outcome #9], Intubation and mechanical ventilation [Secondary outcome #15] and Death [Secondary outcome #17]), Fisher's Exact test was used on the full data; and
 - Where there were no events in either stratum (Damage to the nasal septum [Secondary outcome #10], Damage to the nares [Secondary outcome #11], Pneumothorax

Statistical Analysis Plan

“Randomised trial comparing CPAP machines with reusable vs disposable circuits”

diagnosed by X-Ray [Secondary outcome #12], Intra-ventricular haemorrhage (IVH), intra-cranial haemorrhage (ICH), or periventricular leukomalacia (PVL) as diagnosed by cranial ultrasound scan [Secondary outcome #13], $\text{FiO}_2 \geq 60\%$ to maintain SpO_2 at 90-95% for one hour or more, during CPAP treatment [Secondary outcome #14] and, for infants born at 28+0 to 33+6 weeks' gestation, oxygen dependent at 36 weeks' gestation [Secondary outcome #16]), no statistical test was performed.

Other issues

11. **Multiple comparisons:** The principal control for multiple comparisons was the designation of a single primary endpoint.

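### Requiring both a baseline and a 6-hour blood gas left 5 of 51 infants and no statistical test of pH, PaO2 or PaCO2; a rule that also uses single readings would be better, though its gain is unknown.

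*Protocol*

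**What the plan says.** **Analysis rule.** Protocol section 5.2 (Secondary outcomes) gives pH, PaO2 and PaCO2 the same analysis as the primary outcome. That means a longitudinal mixed model with baseline handled through a random intercept, plus a regression at each time point with baseline as a covariate. It then expects that gases "will not be performed on all infants, particularly infants that recover rapidly" and adds: "if so, this analysis will be restricted to change from baseline at the 6-hour reading".

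**What happened.** SAP paragraph 10a states "No testing was performed for Secondary outcome #4" because "there were only five infants who had readings at both baseline and six hours of age". SAP paragraph 8 leaves the descriptive graphs of raw values unchanged, and these include the three gas measures.

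**Collection.** Protocol section 6.2, item 3, says the clinical protocol will specify "The timing of obligatory outcome measurements (baseline, 6, 12, 24, 48 and 72 hours) and how they should be conducted", and its list includes arterial gases. Section 4.5 says that if samples "are not required for clinical management, they will be ceased, so not all readings will be performed for all babies". Section 4.5 schedules gases at 0, 6, 24, 48 and 72 hours. Sections 3.3 and 6.2 also include 12 hours.

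**The concern.** The plan foresees missing gases and answers with an analysis that needs two readings per infant. An infant with a 6-hour gas but no baseline gas contributes nothing, although its 6-hour value bears on the device comparison. In a randomised comparison a baseline value improves precision and helps check balance, but it need not be a condition of entry. The mixed model that section 5.2 prefers could use infants with one reading, provided baseline is treated as one of the responses. The rule replaces that model in the very situation it anticipates.

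At stake are three of the five physiological secondary outcomes (SpO2, respiratory rate, pH, PaO2, PaCO2). No other listed outcome measures pH or PaCO2. SAP paragraph 2b makes the loss more noticeable: it concedes that FiO2, the primary outcome, is hard to interpret when SpO2 is above target, and only 54 of 224 SpO2 readings (24.1%) were within the target range.

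**Working it through.** **Inputs from the documents**
- Planned size: 40 per arm, 0.63 SD, 80% power, 5% alpha (protocol 5.1).
- Achieved size: 51 infants (SAP 2a).
- SpO2 readings at 6 hours: 50 (SAP 2b).
- Infants with paired gases: 5, arm split not given (SAP 10a).
- Infants with a 6-hour gas only, or a baseline gas only: not given.

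**1. The plan's own figure.** Detectable difference = (1.96 + 0.84) × sqrt(2/40) = 0.626 SD, or 0.634 SD by the t distribution. The stated 0.63 SD is reproduced, with a two-sided test.

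**2. Share of infants kept.** 5/51 = 9.8%, against 50 SpO2 readings at the same time point.

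**3. What five infants could show.** The standard error of an arm difference, in SD units, is sqrt(1/n1 + 1/n2). The smallest exact two-sided rank p-value is 2/C(5, n1).

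| Split (assumed) | Standard error | Smallest p | Detectable at 80% power | Power for 0.63 SD |
|---|---|---|---|---|
| 2 v 3 | sqrt(1/2 + 1/3) = 0.91 | 2/10 = 0.20 | 3.9 SD | 8% |
| 1 v 4 | sqrt(1/1 + 1/4) = 1.12 | 2/5 = 0.40 | 4.8 SD | 7% |

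Stratifying by gestation can only reduce the number of possible arrangements, so van Elteren's test could not do better. If all five were in one arm there would be nothing to compare. Not testing was therefore reasonable for the set that the rule left.

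**4. What a less demanding rule might give.** The number of infants with a 6-hour gas is an assumption here. The table compares 6-hour values without baseline adjustment (t-test, two-sided 5%). Values and change scores have the same SD if the baseline-to-6-hour correlation is 0.5, which is also assumed.

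| 6-hour gases (assumed) | Standard error | 95% CI half-width | Detectable at 80% power | Power for 0.63 SD |
|---|---|---|---|---|
| 8 (4 v 4) | 0.71 SD | 1.7 SD | 2.4 SD | 12% |
| 15 (7 v 8) | 0.52 SD | 1.12 SD | 1.57 SD | 20% |
| 25 (12 v 13) | 0.40 SD | 0.83 SD | 1.17 SD | 33% |
| 51 (25 v 26) | 0.28 SD | 0.56 SD | 0.80 SD | 60% |

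Even if every infant had a 6-hour gas, the test would fall short of the planned 80% power for 0.63 SD.

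**5. Can five pairs support a joint model?** Only paired infants inform the within-infant correlation. If the observed r were 0.5 with n = 5, Fisher's z is 0.549 with standard error 1/sqrt(5 − 3) = 0.707. The 95% interval for z is 0.549 ± 1.386, so r runs from −0.68 to 0.96. The correlation is barely identified, so the fix needs a fallback.

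**6. Which six hours?** SAP 10a counts readings at six hours of age. Protocol 3.3 counts from treatment commencement. Inclusion criterion (d) in section 3.1 allows entry up to 24 hours of age, so the two can differ, and the count of five may depend on which was used.

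**The case against.** The strongest reply is that the rule may not be the cause. Section 4.5 lets sampling stop when care does not require it, so there may have been few gases to analyse under any rule. This stands: without counts of unpaired readings, the loss cannot be attributed to the rule.

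A reader might also infer that the plan chose the method most sensitive to missing data. The documents do not support that. Gaps were expected mainly in infants who recover quickly, and 6 hours is the earliest post-baseline time, so it is the one least exposed to stopped sampling. Nor is the loss peculiar to change scores: a regression with baseline as a covariate would also drop infants without a baseline gas.

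Next, randomisation does not fully protect a comparison among sampled infants. Sampling followed clinical need under unblinded care, so the infants with a 6-hour gas are a post-randomisation selection that could differ by device. This also stands, but it applies equally to the paired set, so it is a reason for an exploratory label rather than for the paired rule.

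Finally, these are secondary outcomes without multiplicity control in a trial that the SAP calls exploratory, and the SAP was updated after recruitment ended. Any new model would be a further post hoc change. That limits the weight of the point but does not remove it. On collection, section 6.2 only lists what a later clinical protocol is to specify, so that conflict is the smaller part of the point.

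**Conclusion.** The point holds as a modest improvement to the analysis rule. The paired rule kept 5 of 51 infants (9.8%), too few for any exact two-sided rank test to reach 0.05, and three gas outcomes went untested. A rule that also uses infants with one reading cannot use fewer infants and relies on data already collected.

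Two stronger readings are not supported. One is that the rule by itself destroyed the gas comparison: sparse sampling contributed, and the size of any gain cannot be computed from the documents. Under the assumed counts of 8 to 25 six-hour gases, the 95% CI half-width runs from 1.7 to 0.83 SD, so the practical conclusion on gases might hardly change. The other is that the arms were not compared at all: raw values were to be graphed, and what is missing is a statistical test.

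Separately, section 4.5 conflicts with sections 3.3 and 6.2 on collection. This review takes no view on which is right.

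**What to change.** **Analysis (protocol 5.2, SAP 10a).** Keep the 6-hour time point but do not require a baseline gas. For each gas measure, model the baseline and 6-hour readings jointly, with arm means constrained equal at baseline and gestational stratum as a factor, so that an infant with either reading contributes. If there are too few pairs to estimate the correlation, compare the 6-hour values with van Elteren's test.

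**Reporting.** Give the number of infants sampled by arm and time, and the 6-hour difference with a 95% CI. Label the result exploratory, and say that sampling followed clinical need under unblinded care and that the analysis was added after recruitment ended. Even if nothing can be tested, the counts would show readers why.

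**Wording.** Clarify whether the count of five in SAP 10a refers to six hours of age or six hours after treatment commencement. Reconcile section 4.5 with sections 3.3 and 6.2 on whether scheduled gases are obligatory and whether a 12-hour gas is taken.

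**Cost.** One further model or test per gas measure on existing data, one table of counts, and a few lines of text. The sampled infants remain a selected group, as they would be under the paired rule.
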